### Table 5. Population epidemiology: estimates of seroprevalence and cumulative incidence by center and year/season, for each IgG assay

Cumulative incidence is seroprevalence adjusted for sensitivity, specificity, and cross-reactivity. The overall estimate will combine all sources of data (see *Appendix 6*).

Centre, Year/season		ZIKV	DENV	CHIKV
	Number ever IgG tested	N		
IgG test 1	Number +ve on first test	R		
	Observed seroprevalence	P=R/N (95% Confidence interval)		
	Cumulative incidence (adjusted)			
	Number ever IgG tested	N		
IgG test 2	Number +ve on first test	R		
	Observed seroprevalence	P=R/N (95% Confidence interval)		
	Cumulative incidence (adjusted)			
	Number ever IgG tested	N		
etc.	Number +ve on first test	R		
	Observed seroprevalence	P=R/N (95% Confidence interval)		
	Cumulative incidence (adjusted)			
Cumulative incidence fro	m all sources combined			

38

Author: [name] (UNIVBRIS)

Table 6. Women's follow-up study: spectrum of initial symptoms in pregnant women and not-pregnant controls, by center

Symptoms		ZI	KV			DE	NV			СН	IKV		
	Preg	nant	Ν	ot	Preg	nant	N	ot	Preg	nant	N	ot	
			preg	nant			preg	nant			preg	nant	
	N	%	N	%	N	%	N	%	N	%	N	%	
Symptom 1													Covariates in regression analyses
Symptom 2													
"													Primary vs secondary infection
"													Co-infection
Symptom combination 1													Previous infection with same or
Symptom combination 2													different arboviruses
"													
"													
Meets clinical criteria 1													
Meets clinical criteria 2													
"													
"													
No symptoms													

Author: [name] (UNIVBRIS)

39

### Table 7. Risk factors for symptomatic vs asymptomatic presentation

	symptomatic	asymptomatic	Univariate Odds ratios (95% CI)	Multivariate odds ratios (95% CI)
Centre				
1			1.0 (ref)	1.0 (ref)
2			2.0 (10.1)	1.0 (1.0.1)
3				
0.0				
Maternal age			1	 
<20				
20-24				
25-29			1.0 ( 0)	10(0)
30+			1.0 (ref)	1.0 (ref)
Pregnant				
Yes				
No			1.0 (ref)	1.0 (ref)
Infection				
ZIKV				
DENV				
CHIKV			1.0 (ref)	1.0 (ref)
Previous infection	1	1	T	T
ZIKV				
DENV				
CHIKV			1.0 (ref)	1.0 (ref)
Mother's education	on			
0-4				
5-9				
10+			1.0 (ref)	1.0 (ref)
etc				
CIL				

Author: [name] (UNIVBRIS)

40

### Table 8. Women's cohorts: Completeness of follow up

		Recruitment	1m	4m	9m	12m
	Number of women					
ZIKV	Contributing data					
	Number lost to Follow-					
	ир					
	Number of women					
DENV	Contributing data					
	Number lost to Follow-					
	ир					
	Number of women					
CHIKV	Contributing data					
	Number lost to Follow-					
	ир					
Not	Number of women					
infected	Contributing data					
	Number lost to Follow-					
	ир					

Author: [name] (UNIVBRIS)

41

[figure not shown]
Table 9. Women's follow-up study - Natural history subsequent to initial presentation. Risk factors for a single specified clinical outcome.

sted Adjusted (95% CI) Rel Risk (95% CI)		Control	Cases	Risk factor
·	•			Infection
				ZIKV
				CHIKV
				DENV
1.0 (ref)	1			No infection
			nset	Pregnant at symptom of
				Yes
1.0 (ref)	1			No
			come onset	Pregnant at clinical outc
				Yes
1.0 (ref)	1			No
				Initial symptoms
				Yes
1.0 (ref)	1			No
				Mother's Age
				<19
				20-24
				25-29
1.0 (ref)	1			30+
		x infection	 r to the inde	Previous infection, prior
				ZIKV
				CHIKV
				DENV
1.0 (ref)	1			No infection
ef)	1			CHIKV DENV

Author: [name] (UNIVBRIS)

42

Figure 1. Schematic influence diagram. Showing the relationships between data and parameters in an analysis of vertical transmission rate and risk of clinical outcomes of vertical transmission. Rectangles denote data and ellipses parameters. Subscript *i* denotes mother-child-specific items, (t) denotes dependency on gestational age. Mother-child data and parameters are outlined in red. Items outlined in green and green influence arrows apply only in analyses which include adjustment for sensitivity, specificity and cross-reactivity of persistence tests.

Author: [name] (UNIVBRIS)

43

### APPENDIX 1. ZIKAction Diagnostics Expert Group

Remit: Within the ZIKA-VT work package, the ZIKAction Diagnostics Expert Group will be responsible for:

- 1. Deciding with collaborating centers which tests will be used "on-line" in ZIKAction to identify women and newborns for follow-up, and which further tests will be undertaken for the later statistical analyses
- 2. Keeping under review the performance characteristics of virological and serological tests used in ZIKAction, including, sensitivity, specificity, cross-reactivity; duration of response to current and/or previous infection; keeping under review the impact of previous infection by the same or different arboviruses on these parameters.
- 3. Formulating algorithms for: the interpretation of sequences of test results (for example, how to treat a lone IgG –ve in a sequence of IgG+, or vice versa; how to interpret a ZIKV IgM+ DENV IgM+ sample.
- 4. Reviewing "odd" sequences of test results which lie outside the formulated algorithms, and deciding how these will be treated.

# APPENDIX 2. Role of Sensitivity, Specificity, Cross-reactivity in estimating gestational age at infection

We denote sensitivity, specificity, and cross-reactivity as Se, Sp, Xr. Cross-reactivity of, say, ZIKA IgM, is a special kind of false positive rate, in which a positive result on ZIKA IgM is obtained in a person who has not had a recent ZIKV infection but has had a recent DENV infection. For clarity, we distinguish this from other failures of specificity, although they too may be the result of cross-reactions.

The incidence *per week* of ZIKV infection in week t of pregnancy is  $\lambda(t)$ , so that the probability of an infection during t is  $1-e^{-\lambda t}$  and the probability of an infection during a period  $(t_1,t_2)$  is

$$1-e^{-\sum_{t_1\leq u\leq t_2}\lambda(u)}$$

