8.1.6 Incidence of primary infections estimated by increase in seroprevalence. If we know or can estimate the cumulative incidence at a starting point T, then cumulative incidence at time t is related to incidence between t and T as follows:

$$\pi(t) = \pi(T) + (1 - \pi(T) \left( 1 - \exp\left( -\sum_{T \le u \le t} \lambda(u) \right) \right)$$

This can be modelled, for example assuming piece-wise constant incidence.

For DENV infection, which has been present for much longer, it may be preferable to model age-and time-specific cumulative incidence:

$$\pi(a,t) = \pi(a,T) + (1-\pi(a,T)\left(1-\exp\left(-\sum_{T \le u \le t} \lambda(a-T+u,u)\right)\right)$$

Using data from pregnant women, we would model incidence from time T and age 16 upwards.

These calculations assume that cumulative incidence can be estimated by adjusting seroprevalence for sensitivity and specificity as shown in *Section 8.1.2* 

8.1.7 Alignment with surveillance data: population estimates of incidence. Once estimates of incidence are available, they can be aligned with surveillance reports to estimate the proportion of incident infections (symptomatic or not) that are reported to the surveillance system. "Alignment" should be interpreted as putting the dates of the tests on the real timescale, so that incidence estimates for ZIKV, DENV, and CHIKV based on ZIKA-VT data can be compared to numbers of cases notified to national or regional surveillance centers, both confirmed and suspected.

If the estimated incidence in some period t is  $\lambda(t)$  and M(t) cases are reported in, say, the population of adult women aged 16-44, over the same time period and from the same area where ZIKA-VT is recruiting, then we can calculate the proportion of all infections that were reported over that time period as :

$$\theta(t) = \frac{M(t)}{N(1 - e^{-\lambda(t)})}$$

Where N is the relevant population size. This quantity can be examined over time to see if it remains relatively stable, and can be used in analyses of test persistence and adjustments for sensitivity and specificity needed to estimate the gestational age of maternal infection and vertical transmission rate (see Sections 5,7).

Further, once an estimate  $\theta(t)$  is available, it can be used to "gross-up" counts M(t), to estimate the true number of infections on a national or regional basis:  $M(t)/\theta(t)$ .

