#### A2.1 A single ZIKV IgM+ DENV IgM- test

To illustrate, we explore the implications of potentially false positive ZIKV IgM tests which cannot be attributed to DENV. To simplify we assume the DENV IgM is perfectly sensitive so that the -ve result rules out a DENV infection.

We assume a single ZIKV IgM+ DENV- test at week 20, and ask: what is the probability there has been a true maternal infection between weeks -2 and week 20, given a Z+D- IgM result at week 20? This quantity can be written as  $p(I_{Z,-2:20} \mid Z+D-_{20})$ . Let  $p(\overline{I}_{Z,-2:20})$  be the probability of no ZIKV infection between weeks -2 and 20. Using Bayes Rule, we expand the formula in section 7.4.5 to allow for imperfect test accuracy:

44

Author: [name] (UNIVBRIS)

$$\begin{split} p\Big(I_{Z,-2:20} \mid Z + D -_{20}\Big) &= \frac{p\Big(Z + D -_{20} \mid I_{Z,-2:20}\Big).p\Big(I_{Z,-2:20}\Big)}{p\Big(Z + D -_{20} \mid I_{Z,-2:20}\Big).p\Big(I_{Z,-2:20}\Big) + p\Big(Z + D -_{20} \mid \overline{I}_{Z,-2:20}\Big).p\Big(\overline{I}_{Z,-2:20}\Big)} \\ &= \frac{\displaystyle\sum_{-2 \leq u \leq 20} F(22 - u).Se\bigg(1 - e^{-\sum_{-2 \leq u \leq 20} \lambda(u)}\bigg)}{\displaystyle\sum_{-2 \leq u \leq 20} F(22 - u).Se\bigg(1 - e^{-\sum_{-2 \leq u \leq 20} \lambda(u)}\bigg) + (1 - Sp).e^{-\sum_{-2 \leq u \leq 20} \lambda(u)}} \end{split}$$

To calculate  $\pi_i(t)$  in this case, we have two components: one for the period up to the IgM+ result, the other after it:

$$\pi_{i}(t) = \begin{cases} \frac{\sum_{-2 \le u \le 20} F(22 - u).Se\left(1 - e^{-\sum_{-2 \le u \le 20} \lambda(u)}\right)}{\sum_{-2 \le u \le 20} F(22 - u).Se\left(1 - e^{-\sum_{-2 \le u \le 20} \lambda(u)}\right) + (1 - Sp).e^{-\sum_{-2 \le u \le 20} \lambda(u)}} & -2 \le t \le 20 \\ 1 - e^{-\lambda t} & 21 \le t \le G_{i} \end{cases}$$

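### Appendix 2 states the weekly infection probability wrongly, and its branch after the IgM+ test leaves out the chance that the woman was already infected

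*SAP*

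**What the plan says.** The opening of Appendix 2 introduces a weekly rate: the incidence per week "of ZIKV infection in week t of pregnancy is" λ(t). The sentence goes on "so that the probability of an infection during t is" 1−exp(−λt), and then gives the probability over a period (t1, t2) as 1−exp(−Σλ(u)), summed over the weeks of the period.

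A2.1 takes a single ZIKV IgM+ DENV IgM− result at week 20. It derives p, the probability of infection in weeks −2 to 20 given that result. It then builds π_i(t), for which "we have two components: one for the period up to the IgM+ result, the other after it". The second component, for weeks 21 to G_i, is 1−exp(−λt) with no other factor.

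Section 8.1.7 considers a period t in which M(t) "cases are reported in, say, the population of adult women aged 16-44, over the same time period", and divides by N(1−exp(−λ(t))). There the probability of infection in one period has λ(t) in the exponent.

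Section 7.1 defines π_i(t) as the probability that the onset of the woman's infection fell in week t, and sums V(t)π_i(t) to obtain her transmission probability v_i. Section 7.6 names Appendix 2 as the source of the adjustment for false positives and false negatives.

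**The concern.** There are two separate faults.

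- **The exponent.** A weekly rate multiplied by t is a cumulative hazard over t weeks, so 1−exp(−λt) is not the risk within week t. It is also negative at t = −2 and −1 and zero at t = 0, all of which lie inside the SAP's own window for onset.
- **The conditioning.** If π_i(t) describes one onset, mass can go to week t > 20 only to the extent that the woman was uninfected through week 20, given her positive test, and stayed uninfected from week 21 to t−1. The printed branch has neither factor. A woman who is probably infected by week 20 is given the full background risk again.

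The values of π_i(t) enter v_i in section 7.1, the severe-outcome model in 7.2, and the trimester probabilities that 7.7 carries into Tables 3 and 4. Section 7.7 lets those probabilities sum to less than one, because infection may fall outside pregnancy. It gives no room for a sum above one.

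**Working it through.** The SAP prints no value of π_i(t), so there is no figure to reproduce. The check uses the SAP's illustrative inputs and labelled assumptions.

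**Inputs**
- Proportion infected in pregnancy, R: 1% and 10% (section 7.6); 20% is an assumption.
- IgM specificity, Sp: 95% (7.6); 99% is an assumption.
- Sensitivity, Se: 95% (7.6, where it is given for the testing algorithm).
- Share s of infections in weeks −2 to 20 still IgM+ at week 20: 12/23 = 0.52, from the mean persistence of about 12 weeks in 8.2.3 over a 23-week window; 1.0 (full persistence) is an assumption.
- Constant λ over the 43 weeks from −2 to 40, with G_i = 40: assumptions. Then λ = −ln(1−R)/43, which is 0.00245 per week at R = 10%.

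**Step 1: internal consistency.** Setting t1 = t2 = t in the period formula gives 1−exp(−λ(t)), which agrees with 8.1.7 and not with the printed weekly form. The weeks −2 to 40 sum to 817. At R = 10% the printed weekly terms therefore imply 1−exp(−0.00245×817) = 86% infected over the window, against 10% from the period formula.

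**Step 2: the printed exponent taken literally, R = 10%.**
- Week 21: 1−exp(−0.00245×21) = 0.050.
- Week 40: 1−exp(−0.00245×40) = 0.093.
- Sum over weeks 21–40: 1.44.
- With λ(t) in the exponent, each week is 0.00245 and the sum is 20×0.00245 = 0.049.

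**Step 3: λ(t) restored, conditioning examined.** By Bayes' rule, with H = 23λ,

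p = s·Se·(1−e^(−H)) / [s·Se·(1−e^(−H)) + (1−Sp)·e^(−H)].

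At R = 10%, Sp = 95% and s = 0.52: p = 0.0272/(0.0272+0.0473) = 0.365. The conditional mass over weeks 21–40 is (1−p)(1−e^(−20λ)) = 0.635×0.0478 = 0.030. The unconditional sum is 0.049, a ratio of 1.6. Nearly all of the gap comes from the missing 1−p (1/0.635 = 1.57). The missing survival from week 21 adds about 2% (0.0489/0.0478).

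| R | Sp | s | p | Unconditional, weeks 21–40 | Conditional, weeks 21–40 | p + unconditional |
|---|---|---|---|---|---|---|
| 1% | 95% | 0.52 | 0.051 | 0.0047 | 0.0044 | 0.055 |
| 10% | 95% | 0.52 | 0.365 | 0.049 | 0.030 | 0.414 |
| 10% | 95% | 1.0 | 0.524 | 0.049 | 0.023 | 0.573 |
| 10% | 99% | 0.52 | 0.742 | 0.049 | 0.012 | 0.791 |
| 10% | 99% | 1.0 | 0.846 | 0.049 | 0.007 | 0.895 |
| 20% | 99% | 0.52 | 0.863 | 0.104 | 0.014 | 0.966 |
| 20% | 99% | 1.0 | 0.923 | 0.104 | 0.008 | 1.027 |

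The inflation grows as the test becomes more reliable, because 1−p then shrinks.

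**The case against.** **The exponent is a slip that the text resolves.** Appendix 2 defines no constant λ, and the adjacent period formula shows what was meant. A bracket or subscript may also have been lost when the file was read. This largely stands. Against it, the same form appears in both the Appendix 2 opening and A2.1, while λ(t) and λ(u) are intact beside it. The text needs correcting, but a reader should not infer that the analysis will really use weekly risks some 20 to 40 times too large. That reading, and the sum of 1.44, hold only if the formula is coded literally.

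**Appendix 2 is illustrative.** A2.1 treats one isolated test under declared simplifications. A2.3 leaves the method for sequences of tests open, and 7.6 says only that adjustment may be needed and must rest on the whole algorithm. This limits how far the fault reaches: A2.1 is not the final estimator for women tested repeatedly. It does not excuse the formula. The only simplification that A2.1 declares is a perfectly sensitive DENV IgM, 7.6 points to this appendix for the adjustment, and A2.3 presents longer sequences as an extension of the same calculation.

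**The remaining error is small at the SAP's own figures.** This stands for 1% incidence. At 10% it is an excess of about 0.02 spread over 20 weeks. A reader might also infer that women's totals will routinely pass one, or that infections will be shifted to the third trimester. The documents support neither. A total above one needs incidence and accuracy beyond the SAP's examples, and the net shift cannot be stated while the branch for weeks −2 to 20 is itself defective.

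**Conclusion.** The formula is wrong as written under either reading of the exponent. The printed 1−exp(−λt) contradicts both the period formula beside it and section 8.1.7, and is probably a notation slip. The absence of conditioning is a fault in its own right, and no other part of the SAP supplies the missing factor.

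With λ(t) restored, the post-test mass at 10% incidence is 0.049 where it should be about 0.030 at 95% specificity. At 99% specificity it should be 0.012, or 0.007 under full persistence. At 1% incidence and 95% specificity the difference is negligible. In the cases tabulated, a total above one arises only at 20% incidence with 99% specificity and full persistence, all three assumed.

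These sizes rest on constant incidence, delivery at week 40, sensitivity of 95%, and a p computed as a proper probability rather than from the printed expression. The point is worth correcting before code is written from the appendix. It does not show that the final transmission estimates will be biased by these amounts.

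**What to change.** 1. Write 1−exp(−λ(t)) in the opening of Appendix 2 and in the second branch of A2.1.
2. For t > 20, set π_i(t) = [1 − p(I_{Z,−2:20} | Z+D−_20)] × exp(−Σ_{u=21}^{t−1} λ(u)) × (1−exp(−λ(t))).
3. Compute p(I_{Z,−2:20} | Z+D−_20) as a proper probability. The printed expression for weeks −2 to 20 needs its own correction: it multiplies by an unweighted sum of F over 23 weeks, and it gives the same whole-window value to every week in the branch. Without this, step 2 inherits the fault.
4. Carry the same conditioning into the extension to sequences of tests in A2.3, and add a check in the code that Σπ_i(t) does not exceed one for any woman.

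The cost is two formula edits here plus the separate correction of the earlier branch. Design, data collection and testing schedule are unaffected.

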#### A2.1 A single ZIKV IgM+ DENV IgM- test

To illustrate, we explore the implications of potentially false positive ZIKV IgM tests which cannot be attributed to DENV. To simplify we assume the DENV IgM is perfectly sensitive so that the -ve result rules out a DENV infection.

We assume a single ZIKV IgM+ DENV- test at week 20, and ask: what is the probability there has been a true maternal infection between weeks -2 and week 20, given a Z+D- IgM result at week 20? This quantity can be written as  $p(I_{Z,-2:20} \mid Z+D-_{20})$ . Let  $p(\overline{I}_{Z,-2:20})$  be the probability of no ZIKV infection between weeks -2 and 20. Using Bayes Rule, we expand the formula in section 7.4.5 to allow for imperfect test accuracy:

44

Author: [name] (UNIVBRIS)

$$\begin{split} p\Big(I_{Z,-2:20} \mid Z + D -_{20}\Big) &= \frac{p\Big(Z + D -_{20} \mid I_{Z,-2:20}\Big).p\Big(I_{Z,-2:20}\Big)}{p\Big(Z + D -_{20} \mid I_{Z,-2:20}\Big).p\Big(I_{Z,-2:20}\Big) + p\Big(Z + D -_{20} \mid \overline{I}_{Z,-2:20}\Big).p\Big(\overline{I}_{Z,-2:20}\Big)} \\ &= \frac{\displaystyle\sum_{-2 \leq u \leq 20} F(22 - u).Se\bigg(1 - e^{-\sum_{-2 \leq u \leq 20} \lambda(u)}\bigg)}{\displaystyle\sum_{-2 \leq u \leq 20} F(22 - u).Se\bigg(1 - e^{-\sum_{-2 \leq u \leq 20} \lambda(u)}\bigg) + (1 - Sp).e^{-\sum_{-2 \leq u \leq 20} \lambda(u)}} \end{split}$$

To calculate  $\pi_i(t)$  in this case, we have two components: one for the period up to the IgM+ result, the other after it:

$$\pi_{i}(t) = \begin{cases} \frac{\sum_{-2 \le u \le 20} F(22 - u).Se\left(1 - e^{-\sum_{-2 \le u \le 20} \lambda(u)}\right)}{\sum_{-2 \le u \le 20} F(22 - u).Se\left(1 - e^{-\sum_{-2 \le u \le 20} \lambda(u)}\right) + (1 - Sp).e^{-\sum_{-2 \le u \le 20} \lambda(u)}} & -2 \le t \le 20 \\ 1 - e^{-\lambda t} & 21 \le t \le G_{i} \end{cases}$$

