#### 7.1 Vertical transmission rate

Assume that for each woman i we will have estimates of the probability  $\pi_i(t)$  that the onset of her infection occurred in week t. We assume that vertical transmission can only occur if infection exists during pregnancy, so that the *onset* is in the interval  $-2 \le t \le G_i$  where  $G_i$  is the gestational age at delivery. If the probability of vertical transmission given maternal infection at week t is V(t), then the probability of in utero transmission in women i is:

$$v_i = \sum_t V(t)\pi_i(t), \quad Y_i \sim Bern(v_i)$$
(7.1)

The outcome data  $Y_i=0,1$  (1 indicating Vertical infection (VI), 0 indicating no VI in a child born to women i), is a Bernoulli realization of the parameter  $v_i$ . In a Bayesian framework, we can attribute a vague prior to V(t) and use the data obtain posterior distributions for V(t),  $v_i$ , and  $\pi_i(t)$  given the Bernoulli likelihood.

In practice, a smooth parametric or semi-parametric function would be fitted to V(t). The analysis is readily extended to include additional risk factors  $\mathbf{X}_i$  with coefficients  $\boldsymbol{\beta}$ :

$$logit(v_i) = logit(\sum_t V(t)\pi_i(t)) + \boldsymbol{\beta}^T \mathbf{X}_i$$

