#### 7.4 Analysis of gestational age at maternal infection

We start with an analysis that assumes perfect test sensitivity and specificity. The gestational age at the onset of maternal infection is  $\pi_i(t)$ , t in weeks. Although the period of interest is between just before conception and delivery, ie the interval  $-2 \le t \le G_i$ ,  $\pi_i(t)$  is defined over a wider interval  $-2 - D \le t \le G_i + D$ , where D is the maximum duration of a test of persistence. This is because a first IgM+ test D weeks after delivery, or an IgM- test D+2 weeks before conception, both provide information about the probability of infection during pregnancy. Because there may be a finite probability that the maternal infection occurred before conception,  $\sum_{-2 \le t \le G_i} \pi_i(t)$  can take any value

between 0 and 1. Some special cases help clarify the concepts:

7.4.1 Onset of infection marked by symptoms. If a woman has symptoms in pregnancy starting at T then  $\pi_i(t) = 1$ , if t = T and  $\pi_i(t) = 0$ , if  $t \neq T$ .

7.4.2 Seroconversion alone. If the interval is defined by seroconversion during pregnancy, ie between a last lgG- at  $t_1$  and a first lgG+ at  $t_2$ , then in the absence of any other information,

$$\pi_i(t) = 1/(t_2 - t_1 + 1)$$
, if  $t_1 \le t \le t_2$ , else 0.

7.4.3 Surveillance data alone. Alternatively, suppose there are surveillance counts M(t) of suspected or confirmed cases (of ZIKV, DENV, or CHIKV) depending on the disease being studied [4], then the "a priori" distribution of when the infection might have occurred (given that it occurred in pregnancy) can be represented as a Dirichlet distribution:

$$\pi_i(t) = \alpha(t), \quad \alpha(t) \sim Dirichlet(M(t)), \quad -2 \le t \le G_i$$

7.4.4 PCR+ or IgM+, no surveillance data. If the specified interval is defined by a PCR+ or IgM+ test at time  $t_2$  and the earliest possible date of infection was  $t_1$  (which might be marked by an IgM- result, or  $t_1 = t_2 - D$ ) then, if the cumulative persistence distribution (the probability that persistence is d or less weeks) is  $F(d,\theta)$  with parameter(s)  $\theta$ , then (dropping the  $\theta$ ):

Author: [name] (UNIVBRIS)

20

$$\pi_i(t) = \frac{F(t_2 - t)}{\sum_{t_1 \le u \le t_2} F(u - t)}, \text{ if } -2 \le t \le t_2, \text{ else } 0$$

7.4.5 PCR+ or IgM+ with surveillance data. Now we assume the same test results, but surveillance data is available as well:

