The diagnostic algorithm will include confirmatory tests, and it is hoped that the effective specificity and sensitivity of the entire algorithm will be high. However, it may still be necessary to take false positives and negatives into account. Calculations capable of making these adjustments (see Appendix 2) assume that an estimate is available of the absolute a priori risk of infection, based on surveillance data. This is in contrast with the calculations in Section 7.4 which assumed perfect test accuracy, where only the relative probabilities were needed. The reason for this is that the probability that a ZIKV IgM+ is a false positive will be much higher if there is very little ZIKV circulating at the time, and much greater – depending on the cross-reactivity of the test – if there is a high incidence of DENV. Methods for obtaining information on the absolute incidence are explained in Section 8.1.7).

Note that adjustments for sensitivity and specificity need to be based on the properties of the entire algorithm, and on the entire set of results through the pregnancy.

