#### 7.7 How the full analysis will be used

The various components discussed above can be assembled into a single analysis, as shown by the influence diagram (*Figure 1*), providing a single integrated analysis of: test persistence and its covariates; GA at maternal infection; VTR and its risk factors; and risk of severe congenital outcomes and its risk factors.

One of the outputs will be the distribution of maternal GA at infection, in weeks. We will extract the posterior mean probability that a maternal infection occurred during each month, or trimester, and take this forward to be used in analyses along the lines of Tables 3 and 4. In effect the 0,1 "dummy covariates" that would be used in conventional analyses of GA at infection as a risk factor, can then be replaced by a set of probabilities. Note that these cannot exceed one, but they need not add to one, if there is a finite probability that the infection occurred before, or after, pregnancy. Standard

Author: [name] (UNIVBRIS)

25

statistical software can then be used to explore GA at infection as a risk factor, or interactions between GA at age of infection and other risk factors, exactly as if 0,1 covariates were being used.

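### SAP Appendix A2.1 gives every week from -2 to 20 the whole-window probability of infection, computed from an unweighted sum above 1, so π_i(t) is not a distribution and false-positive IgM results are heavily under-discounted

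*SAP*

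**What the plan says.** Section 7.1 defines π_i(t) as the probability "that the onset of her infection occurred in week t" and feeds it into v_i = Σ V(t)π_i(t), a Bernoulli parameter. Section 7.4 states that the sum of π_i(t) over pregnancy lies between 0 and 1. Section 7.7 says of the monthly or trimester probabilities derived from it: "Note that these cannot exceed one, but they need not add to one".

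Section 7.6 sends the reader to Appendix 2 for the correction for imperfect tests: "Calculations capable of making these adjustments (see Appendix 2) assume that an estimate is available of the absolute a priori risk of infection".

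In A2.1 the set-up is "We assume a single ZIKV IgM+ DENV- test at week 20" and the question is "what is the probability there has been a true maternal infection between weeks -2 and week 20". The appendix says that "we expand the formula in section 7.4.5 to allow for imperfect test accuracy". It then gives one ratio:

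P = A / [A + (1-Sp)·exp(-Λ)], with A = Σ F(22-u)·Se·(1-exp(-Λ)),

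where the sum runs over u = -2 to 20 and Λ is the sum of the weekly incidences λ(u) over those weeks. For π_i(t) it then states that "we have two components: one for the period up to the IgM+ result, the other after it". The same ratio is printed a second time as π_i(t) for all t from -2 to 20. After week 20, π_i(t) is the weekly risk alone.

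**The concern.** Two faults show in the printed expressions.

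- **No week index.** The right-hand side of π_i(t) does not contain t. A probability that belongs to the 23 weeks together is given to each of them.
- **No week weights.** The probability of a positive test given infection in the window should average the week-specific detection probabilities, weighted by when infection occurred. A2.1 adds 23 of them and multiplies the total by the whole-window risk. Formula 7.4.5, which A2.1 says it expands, does carry a week weight α(t).

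Section 7.6 treats false-positive IgM as the serious threat to the vertical transmission rate, with underestimation by a factor of 1.5 at 10% incidence and 5 at 1%. Coded as printed, A2.1 would leave much of that bias in place and pass equation 7.1 values that are not probabilities.

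**Working it through.** A2.1 prints no numerical result to reproduce, so its formula was evaluated directly.

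**Inputs from the SAP.** Sp = 95% and infection risk of 10% or 1% (7.6); mean IgM persistence of about 12 weeks (8.2.3); F(d) defined as "the probability that persistence is d or less weeks" (7.4.4); test at week 20; 23 weekly terms.

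**Assumptions.** Se = 0.95 (7.6 uses this figure for a whole algorithm); the 10% or 1% risk falls evenly over the 23 weeks; persistence is Weibull with shape 1 or 2. Ranges below cover the two shapes.

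**Step 1, the sum.** ΣF(22-u) = 13.97 (shape 1) or 12.62 (shape 2). Times 0.95 this is 13.27 or 11.99, standing where a probability is required. With F as defined, the sum exceeds 1 for every mean persistence tried from 1 to 52 weeks.

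**Step 2, the printed posterior** (shape 2 shown, shape 1 result after it).

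- 10% risk: 11.99 × 0.10 = 1.199; false-positive term 0.05 × 0.90 = 0.045; 1.199 / 1.244 = 0.964 (shape 1: 0.967).
- 1% risk: 11.99 × 0.01 = 0.120; false-positive term 0.05 × 0.99 = 0.0495; 0.120 / 0.169 = 0.708 (shape 1: 0.728).

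**Step 3, the sum over weeks.** 23 × 0.964 = 22.2 at 10% risk. 23 × 0.708 = 16.3 and 23 × 0.728 = 16.8 at 1% risk. Section 7.4 caps this sum at 1.

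**Step 4, equation 7.1.** With an assumed constant V(t) = 0.05 at 10% risk, v_i = 0.05 × 22.2 = 1.11. The coherent version gives about 0.03.

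**Step 5, the coherent posterior.** Let q(u) be the probability that onset is in week u, and S(u) = 1-F(20-u) the probability of still being IgM+ at week 20. The numerator is B = Σ q(u)·[Se·S(u) + (1-Sp)·(1-S(u))].

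- 10% risk: B = 0.0461–0.0522, and B / (B + 0.045) = 0.51–0.54.
- 1% risk: B = 0.0047–0.0053, and B / (B + 0.0495) = 0.09–0.10.

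Leaving out the second term in the bracket (infected women whose IgM has waned but who test falsely positive) gives 0.49–0.53 and 0.08–0.09.

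| Sp | Risk over weeks -2 to 20 | Printed | Coherent |
|---|---|---|---|
| 95% | 10% | 0.96–0.97 | 0.51–0.54 |
| 95% | 1% | 0.71–0.73 | 0.09–0.10 |
| 95% | 0.1% | 0.19–0.21 | about 0.01 |
| 90% | 10% | 0.93–0.94 | 0.35–0.38 |
| 90% | 1% | 0.55–0.57 | about 0.05 |
| 99% | 10% | 0.99 | 0.83–0.85 |
| 99% | 1% | 0.92–0.93 | 0.31–0.34 |

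For the same F, using a sum where a mean of 23 terms is needed inflates the odds of true infection against false positive about 23-fold.

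**Step 6, does it hinge on F or the time index?** Replacing F(22-u) by 1-F(20-u) but leaving the sum unweighted still gives 0.96 at 10% and 0.67–0.70 at 1%, with weekly values summing to about 22 and 15–16. The missing week weight drives the result.

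**The case against.** The strongest reply is that this is a notation slip in an illustration. A2.1 presents itself as illustrative and simplified, the Bayes expansion on its first line is correct, and u serves both in the outer sum and in the inner exponent. If the inner risk is read as the week-u risk 1-exp(-λ(u)), with F(22-u) kept, the window probability becomes 0.55–0.57 at 10% and about 0.10 at 1%, close to the coherent values. That stands as an explanation of how the error arose. It does not remove it: the only simplification that A2.1 declares concerns DENV IgM sensitivity, 7.6 relies on Appendix 2 for the adjustment, and the same expression is printed twice, so a text-extraction error is unlikely.

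It also stands that a lone IgM+ should not be the usual case, since 7.5.3 provides PCR on all IgM+ results. Section 7.6 wants the adjustment based on the entire algorithm, and A2.3 leaves sequences of tests undetermined. A v_i above 1 would probably stop the program. The quieter risk is a programmer who rescales π_i(t) but keeps the unweighted sum.

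Some stronger readings are tempting but not supported:

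- *False positives are barely discounted everywhere, or most are called true infections.* That fits 10% risk. At 1% the formula removes 27–29% where about 90% is due, and at 0.1% it returns about 0.2.
- *A2.1 is the SAP's only correction for false positives.* A2.2 is a second one for maternal infection, and 8.1.2 and Appendix 6 adjust seroprevalence.
- *The planned vertical transmission analysis is invalid.* The fault lies in an appendix formula. The definitions in 7.1 and 7.4 that it violates are sound.

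**Conclusion.** A2.1 is wrong as written. It prints a whole-window probability as the probability for each week and builds it on a sum that is not a probability, contrary to 7.1, 7.4, 7.7 and the week weighting in 7.4.5. These two faults follow from the printed expressions; for an IgM marker lasting about 12 weeks, they do not depend on the assumed inputs.

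The size does depend on inputs. With Sp = 95% and 12-week mean persistence from the SAP, and the assumed sensitivity, even incidence and Weibull shapes, the printed posterior is nearly double the coherent one at 10% risk and more than seven times it at 1%. The coherent figures are approximate, because they take Sp to cover IgM that persists from infection before week -2. The v_i of 1.11 rests on an assumed V(t).

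Three lesser points change the window probability little. F is a cumulative distribution where the probability of still being positive, 1-F, is needed (also in 7.4.4 and 7.4.5). Elapsed time at a week-20 test is 20-u, not 22-u. The term after week 20 is not reduced for earlier infection: over an assumed 20 further weeks at 10% risk it totals 0.09 against about 0.04.

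The A2.2 formula is broken in the text at hand and cannot be judged.

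**What to change.** Replace the A2.1 expressions before they are coded.

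- Define q(u) = (1-exp(-λ(u)))·exp(-Σ λ from week -2 to u-1) and S(u) = 1-F(20-u).
- For -2 ≤ t ≤ 20: π_i(t) = q(t)·[Se·S(t) + (1-Sp)·(1-S(t))] / {Σ_u q(u)·[Se·S(u) + (1-Sp)·(1-S(u))] + (1-Sp)·exp(-Σ λ over weeks -2 to 20)}. The window probability is the sum of these values.
- For t > 20: multiply 1-exp(-λ(t)) by (1 minus the sum of π_i up to week 20) and by the probability of no infection from week 21 to t-1. Write λ(t) where the appendix prints λt.
- State that Sp is the diagnostic specificity, covering IgM left from infection before week -2, or extend the sum back to week -2-D as in 7.4.
- Use 1-F in 7.4.4 and 7.4.5 as well, and check A2.2 for the same missing week weights.
- Add a programming check that Σ π_i(t) over pregnancy does not exceed 1 for any woman.

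The cost is an appendix revision and the matching code. No data collection changes.
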